Surgical management and anatomical fixation of these injuries is the accepted gold standard treatment due to the incidence of post operative arthritis and poor outcome with malreduction or missed syndesmosis injury.6 Cadaveric studies have demonstrated a reduction in tibiotalar contact area of 45% with one millimetre of talar lateral displacement.⁷ Options for syndesmotic fixation vary and is an ongoing topic for debate. Recent surveys have shown wide variation in practice, with use of one or two 3.5 or 4.5 mm screws, engaging three or four cortices as the most common options. A high proportion of surgeons then routinely remove these at 3 months. 8,9 Routine removal of metallic screw fixation is another debated topic, however, and there are no randomised controlled trials looking at this question. Screw breakage is common, however there is no evidence to suggest this results in worse outcome, on the contrary it may be that intact screws are more problematic and require removal. 10 A general review of this literature concluded that routine removal is probably not indicated, and that the incidence of this is decreasing however still commonplace. 11 Hardware related pain can be seen in 31% of patients and which may explain the high incidence of removal, however improvement following hardware removal can occur in only 50% of patients. 12 Furthermore removal of syndesmosis screws has been shown to have a relatively high complication rate of 22.4%. 13 This explains some of the desire to find alternative options for fixation including bioabsorbable screws and suture button methods.

Evidence for Bioabsorbable screws

Bio-absorbable screws have been shown to have similar biomechanical strength when comparing 5mm tri-cortical single screw fixation of the syndesmosis. ¹⁴ Equal fatigue and failure strength has also been shown with 4.5mm screws. ¹⁵

Three small case series have reported use of these screws with good or excellent outcomes, and maintenance of mortise reduction (n=7,4 and 23). \(^{16,17,18}\) Sinisaari et al showed no significant difference in outcome in 18 patients treated with bioabsorbable screws compared with 12 treated with standard metallic screw fixation. \(^{19}\) Thodarson et al showed no significant difference in a prospective randomised trial between the two methods of fixation in 32 patients (PLA). \(^{20}\) Kaukonen et al reported higher rates of patients returning to previous preinjury activity levels, and less swelling with bioabsorbable screw fixation (PLLA) in a randomised trial of 38 patients. \(^{21}\) Sun et al found a higher rate of foreign body reaction in those treated with bioabsorbable screws (PLLA) in a randomised trial of 168 patients, however functional recovery was similar. \(^{22}\) A meta-analysis on these papers found no significant difference in functional outcome, or complication rate, however overall higher complication rates with bioabsorbable screws. \(^{23}\)

The studies mentioned above have used bioabsorbable screws composed of either Polylactide acid (PLA), or polylevolactic acid (PLLA). The logic behind the design of these screws is that they undergo hydrolysis into lactic acid and glycolic acid which in turn are further broken down and excreted by the body. PLA and PLLA lose their mechanical resistance from 3 months to 1 year, with PLLA degrading slower the PLA.²⁴ PLLA can have a resorbtion time of over 5 years and there has been question to whether this can even be classified as bioabsorbable.²⁵ There has been concern historically with foreign body reactions, sterile abscess formation, sinus tract, fistula formation and osteolysis relating to some bioabsorbable implants, particularly PGA screws which can have a faster resorbtion time of 4-8 weeks.²⁶

This study proposes to use a 5th generation bioabsorbable screw (Activascrew[™], Bioretek) which is a co-polymer of PLLA and PGA; poly L-lactide-co-glycolide (PLGA). This should maintain mechanical strength for at least 8 weeks and bioresorb within 2 years. ²⁷ Modulus of stiffness is similar to bone and allows gradual transfer of load during resorbtion. This is ideal for fixation of the syndesmosis, allowing for healing in a reduced position, then undergoing resorbtion to allow the small increments of movement that happen normally at the syndesmosis and removing the need for removal of metalware in a second operation.

Study Aim

Primary objective

To assess syndesmosis fixation and maintenance of reduction, with bioabsorbable screws, measured with CT scanning immediately post operatively and at one year post operatively.

Secondary objectives

- To identify patient reported outcome scores in the first year after the injury
- To identify the length of procedure
- To identify the duration of image intensifier use
- To measure complication rates in the first year after injury
- To measure range of movement and functional scoring
- To measure pain scores in the first year after the injury
- Weight bearing distribution test

Surgical Technique

The operation requires the patient positioned supine with a sandbag beneath the ipsilateral buttock to internally rotate the leg to permit the ankle and foot to sit in neutral. Appropriate antibiotics as per local guidelines should be administered prior to insufflation of a tourniquet. Fluoroscopy is required throughout the procedure and should be positioned on the contralateral side to the injured limb to improve the access for the surgical team.

Depending on the injury type the fibula may or may not require fixation (maissoneuve or weber B/C type injury). This will be performed if necessary via a direct lateral approach to the fibula, and fixation as per surgeon preference appropriate for the fracture configuration. Typically a lag screw and one-third tubular neutralisation plate is used. Plates should be applied to the posterolateral surface of the fibula to permit passage of the syndesmosis screw through the plate and for increased mechanical stability. Following this the syndesmosis will be reduced with the foot plantigrade using large pointed reduction forceps with or without a K-wire. Medial malleolar fixation, if required, is performed after fibula fixation.

Bio-absorbable screw fixation

A single 4.5 mm fully threaded Activascrew[™] (2094913CE01) is placed through four cortices if the fibula fracture is being fixed, through the plate if feasible. Two are used in the case of high fibula or maissoneuve injuries. These will all be through four cortices. A countersink may be used. The screws should be placed parallel to the tibial plafond, 2-4cm proximal to the tibio-talar joint and 30° from posterior to anterior. In the case of fibula

fixation this should be though the plate if feasible. The reduction of the syndesmosis and appropriate placement of the positioning screw(s) should be checked intra-operatively with fluoroscopy. The syndesmosis is reduced, using reduction forceps. A hole is drilled with the 3.5mm drill, then tapped with the 4.5mm tap and measured. The ActivascrewTM holder and screwdriver are used to pick up and insert the desired screw. Once the screw is in position the insertion adapter is removed and discarded.

Standardised rehabilitation protocol

Post operatively the patient remains non weight-bearing in a Plaster for a total of 6 weeks with a cast change, wound check and removal of sutures at 2 weeks. Following this the patient would then remain partial weight bearing in a protective boot for a further 6 weeks. The patients should be prescribed 6 weeks of Low Molecular Weight Heparin for venous thromboembolic prophylaxis as per local protocol.

Study Design

Please see appendix 1 for information on how the study will be run during the COVID-19 pandemic.

Sample size considerations

A total number of 40 patients should be sufficient to assess the outcome of fixation using this device.

Patients selection and enrolment

Patients will be thoroughly screened to assess their suitability for the study and must fit the inclusion and exclusion criteria.

Inclusion criteria

- Patient has a Weber C fibula fracture with or without a medial malleolus fracture and evidence of radiological syndesmotic widening on intra-operative stressing
- Patient has a Weber B fracture with evidence of syndesmosis widening radiologically on stressing intra-operatively
- Patient has a maissoneuve type injury with evidence of syndesmotic diastasis
- Patient mobilises independently, with or without aids.

- Patient has given formal consent to be involved in the trial and has completed the study consent form
- Patient is likely to comply with study requirements
- Age range of patients in the study is 18-64 (inclusive).

Exclusion criteria

- **Immobility**
- Presence of a posterior malleolus fracture involving >25% of articular surface
- Open fractures
- Pathological fractures
- Other fractures involving the same lower extremity
- Patient unwilling to give informed consent to be included in the trial
- Patient has other injuries that would influence the study
- Any ankle fracture that the treating surgeon feels inappropriate to be included in the study

Outcome measures

Primary Outcomes

CT Scanning

All patients will undergo focused CT scanning two weeks post operatively and at one year. A customised foot holding device will enable to scan to be taken with both feet in neutral alignment (Evolution supine foot positioner, Vasocare Ltd). Assessment will be made in comparison with the contralateral side to assess reduction of the syndesmosis. Quantative measurement of reduction will be measured using the technique as described by Phisitkul et al.²⁸

Secondary Outcomes

Peri-operative

- Procedure duration
- X Ray exposure duration

Ability to weight bear

Assessment of ability to load share on the affected limb on initial weight bearing and the change in weight distribution on timed weight bearing over a 60 second period. Measured using scale analysis, with the patient being blinded to the readings

Complications

- Surgical Wound Review for delayed or complicated wound healing
- **Secondary Operations**
- Adverse events

Patient Reported Outcome Scores:

Visual Analogue Scale (VAS).

- Patients will be divided into the following categories;
 - Mild or no pain: 0-3
 - Moderate pain: 4-7
 - Severe pain: 8 10.

American Academy Orthopaedic Surgeons Foot & Ankle Outcomes²⁹

A validated, self- administered outcome questionnaire. It involves 25 questions regarding foot and ankle health from patient's perspective. There are 5 subscales: pain (9 questions), function (6 questions), stiffness and swelling (2 questions), giving way (3 questions), and shoe comfort (5 questions). It has good usability, reliability and validity.

Olerud and Molander Ankle Score³⁰

a self-administered patient questionnaire. It is a good outcome tool for assessing symptoms after an ankle fracture. The score is based on nine different items: pain, stiffness, swelling, stair climbing, running, jumping, squatting, supports and work/activities of daily living. The scoring system correlates well with parameters considered to summarise the results after this type of injury and is therefore recommended for use in scientific investigations.

EuroQol EQ-5D31

a validated, generic health-related quality of life measure consisting of 5 dimensions each with a 3-level answer possibility. Each combination of answers can be converted into a health utility score. It has good test-retest reliability, is simple for patients to use, and gives a single preference-based index value for health status that can be used for broader cost-effectiveness comparative purposes.

Assessment methods

Pre Clinical Evaluation

Demographic factors including age, gender, co-morbidities and primary diagnosis will be obtained. A lateral and antero-posterior mortise X ray will be obtained to evaluate and classify fracture

Operative Recording

The lead operator will complete a standardised, structured operation note.

Assessment & Clinical Evaluation

The patients in the study will be asked to attend for follow-up and assessment for 12 months post surgical intervention, as outlined in figure 1.

Data handling

Case report forms (CRFs) will be supplied by the Chief Investigator and all data will be recorded on the case report forms (CRFs). Upon enrolment into the clinical study, a unique Patient Study ID will be assigned in numerical order and will be prefixed by a unique lettered code for different sites. Only the Research Associate (RA) for each site will have the key to identify individual patients.

The RA is responsible for completion of the CRFs in a timely and accurate manner. All CRFs must be legible and completed in black or blue ink. Any necessary corrections are to be made by drawing a single line through the incorrect entry and writing in the revision, beside the relevant box and must be signed and dated by the investigator or his or her representative. Data is not to be obliterated by blacking out, using correction fluid or by erasing the original entry. Any documents related to the study must be archived at the study site or in a central archive. This includes anonymising the identities of the subjects involved in the study. This list and the signed informed consent forms are key documents in the files that need to be stored by the investigator in a secure environment for between 3-7 years, depending upon each participating hospitals current practice.

Time Point Data Collection

Baseline	X Rays, Patient questionnaire, Pre-injury PROMS	
Operation	Classification, operative time and Duration of XR exposure	
2 weeks	X Rays, focused CT of syndesmosis, Wound review, Record of Complications	
6 weeks	X Rays, Wound review, Record of Complications	
3 months	X Rays, OMAS, EQ-5D, AA0S:FA, Weight bearing test, Record of complications	
6 months	OMAS, EQ-5D, AAOS:FA, Weight bearing test, Record of complications	
12 months	X Rays, OMAS, EQ-5D, AAOS:FA, Weight bearing test, Record of complications, focused CT of syndesmosis	

Figure 2; Follow up and data collection outline

Further considerations

Pre-study procedure

Prior to the study commencing, ethics approval will be required.

Patient information

The investigator will provide the patient with written trial information prior to obtaining consent for trial inclusion. The terminology used must be chosen so that the layman can fully understand the content.

Patient's informed consent

Each patient's agreement to participate in the clinical trial must be given in writing. Copies of the written informed consent forms will be inserted into the investigator's study file and in the patient's medical notes. An additional copy will be given to the patient. The patients will be given ample time to consider participating in the clinical evaluation. Patients may withdraw their consent to participate in the trial at any time, and for any reason.

Adverse event management

Adverse events are defined as any untoward medical occurrence in a clinical trial subject and which do not necessarily have a causal relationship with the treatment. Serious adverse events are defined as any untoward and unexpected medical occurrence that:

- Results in death, [SEP]
- Is life-threatening sep

- Requires hospitalisation or prolongation of existing inpatients hospitalisation,
- Results in persistent or significant disability or incapacity, see the
- Any other important medical condition that, although not included in the above, may require medical or surgical intervention to prevent one of the outcomes listed.

All adverse events will be listed on the appropriate Case Report Form for routine return to the central office and all serious adverse events will be entered onto the Serious Adverse Event reporting form and emailed to [name] within 24 hours of the investigator becoming aware of them. Once received, the Chief Investigator will confirm causality and expectedness. Serious adverse events that are deemed to be unexpected and related to the trial will be notified to the Research Ethics Committee within 15 days.

Serious adverse events that may be expected as part of the surgical interventions, and that do not need to be reported to the main Research Ethics Committee are: complications of anaesthesia or surgery (e.g. wound complications, infection, damage to a nerve or blood vessel and thromboembolic events) and secondary operations for infection, mal-union, non-union or for symptoms related to the metalwork.

Trial Report and publications

At the end of the trial a report will be written, which will include a statistical evaluation and an assessment of the results from the medical point of view. The report will be based on the points laid down in this protocol. All grouped patient data will be anonymised.

Study Schedule

Expected date of first inclusion:

01/12/2020

Estimated date of last patient's inclusion

31/12/2024

- Charles M. Court-Brown, Ben Caesar, Epidemiology of adult fractures: A review, Injury, Volume 37, Issue 8, August 2006, Pages 691-697, ISSN 0020-1383, http://dx.doi.org/10.1016/j.injury.2006.04.130.

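### The protocol makes unexpectedness part of the definition of a serious adverse event, contradicting its own later rules on expected serious adverse events

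*Protocol*

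**What the plan says.** Everything at issue is in the protocol section Adverse event management. It first defines an adverse event as an untoward medical occurrence, with no condition about expectedness. The next sentence adds such a condition for serious events: "Serious adverse events are defined as any untoward and unexpected medical occurrence that" one of the listed criteria is met (death, threat to life, hospitalisation and so on).

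The section then sets the reporting path:

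- Routine: "All adverse events will be listed on the appropriate Case Report Form for routine return to the central office".
- Expedited: "all serious adverse events will be entered onto the Serious Adverse Event reporting form", to be emailed within 24 hours of the investigator becoming aware.
- Central assessment: "Once received, the Chief Investigator will confirm causality and expectedness".
- Ethics committee: "Serious adverse events that are deemed to be unexpected and related to the trial will be notified to the Research Ethics Committee within 15 days".
- Exemption: a class introduced as "Serious adverse events that may be expected as part of the surgical interventions, and that do not need to be reported" to the main ethics committee. It covers complications of anaesthesia or surgery, with examples, and secondary operations for certain reasons.

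No other part of the protocol defines an SAE. Appendix 1, on running the study during the pandemic, does not deal with adverse events.

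**The concern.** Seriousness and expectedness are separate properties of an event. Seriousness should decide whether the SAE form is filed. Expectedness should decide what happens to it afterwards. The definition merges the two, while the rest of the section keeps them apart.

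The definition is the first test an investigator applies. Someone who stops there and judges a serious infection to be foreseeable after this surgery will conclude that it is not an SAE and file no 24-hour form. The Chief Investigator's assessment begins on receipt of that form, and the protocol describes no other step at which a local judgement of expectedness is reviewed. If that judgement was wrong, an event that belonged with the ethics committee within 15 days may not get there.

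This matters somewhat more for this device. The protocol's own background section records past concern about foreign body reactions, sterile abscesses, sinus tracts and osteolysis with some bioabsorbable implants. Such a reaction could first be labelled locally as an ordinary wound complication or infection. The Data handling section also provides for several sites, with patient identifiers "prefixed by a unique lettered code for different sites", so different investigators could apply different triggers.

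**Working it through.** No arithmetic applies, and the protocol gives no SAE rate from which to estimate how many events are affected. The check is one of logic: take the definition as written and test each later sentence against it.

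**Step 1: the definition.** SAE = untoward AND unexpected AND meets a seriousness criterion. It follows that the set {SAE AND expected} is empty.

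**Step 2: the later sentences.**

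| Later sentence | What it presupposes | Under the definition |
|---|---|---|
| Class of SAEs that may be expected, exempt from ethics committee reporting | That expected SAEs exist | Contradiction: the class has no members |
| Ethics committee notified of SAEs judged unexpected and related | That some SAEs are expected | Redundant: the word *unexpected* filters nothing |
| Chief Investigator confirms expectedness once the form is received | That expectedness is settled after filing | Out of order: it had to be judged before the form was due |

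Of the three, the first is an outright contradiction. The second is a redundancy. The third is a conflict of sequence, and could at a stretch be read as central confirmation of a provisional local view.

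**Step 3: which events are caught.** The expected class names four example complications (wound complications, infection, nerve or vessel damage, thromboembolic events) and four reasons for a secondary operation (infection, mal-union, non-union, metalwork symptoms): 4 + 4 = 8 listed items. Infection appears in both groups and the complications are given only as examples, so 8 describes the list and does not measure impact. Where such an event is serious and is regarded as expected, the definition excludes it and the later text includes it.

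**Step 4: one event under both readings.** Take a patient admitted to hospital with a thromboembolic event that the investigator regards as foreseeable.

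- By the definition: not an SAE, no 24-hour form, no Chief Investigator assessment triggered.
- By the later text: an SAE, form due within 24 hours, Chief Investigator assesses it, ethics committee notification not needed if it is confirmed as expected.

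**Step 5: what is still captured.** The event remains an adverse event, because that definition has no expectedness condition, and so goes on the Case Report Form. The data collection table also records complications at 2 weeks ("focused CT of syndesmosis, Wound review, Record of Complications"), 6 weeks, 3 months, 6 months and 12 months: 5 of 5 post-operative visits. The secondary objective of measuring complication rates in the first year is therefore not compromised.

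**The case against.** The strongest reply is that the section resolves itself when read as a whole. The closing paragraph explicitly calls infections, thromboembolic events and secondary operations SAEs and exempts them only from ethics committee reporting. The paragraph before sends all SAEs to the 24-hour form. Specific text naming these events should outweigh one adjective in a general definition. One can add that *may be expected* describes types of event while *unexpected* describes a particular occurrence, so an infection can be unforeseen in one patient and still be of a recognised type.

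This shows what the authors probably intended, and a careful reader of the whole section may well file the form. It does not remove the conflict. The definition still excludes events that the later text calls SAEs, and serious events that are foreseeable but not listed have no specific sentence to rescue them. The distinction between types and occurrences would leave the 24-hour duty hanging on whether each investigator found a given infection surprising, which is the judgement the section reserves for confirmation by the Chief Investigator.

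Other objections hold, but only limit the size of the point. Listed events confirmed as expected are not notified to the ethics committee on either reading. The protocol shows no stopping rule or monitoring committee that depends on SAE counts. The number of sites is not stated, and Appendix 1 describes the pathway at one hospital, so divergence between sites is possible rather than shown. The ambiguity can still arise between investigators at a single site.

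**Conclusion.** The concern holds. The SAE definition contradicts the class of expected SAEs in the same section, makes one later qualifier redundant, and puts the expectedness judgement ahead of the step at which the protocol places it. It should be corrected, since it is a stated rule that is wrong as written and not a detail left for elsewhere.

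The consequence is confined to safety oversight: foreseeable serious events could miss the 24-hour form and the Chief Investigator's review of causality and expectedness. This rests on an investigator following the definition literally; how often that would happen cannot be estimated from the protocol. Complication data remain captured, and no endpoint, estimate or sample size is affected.

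**What to change.** Delete the words *and unexpected* from the definition, so that an SAE is any untoward medical occurrence meeting one of the listed criteria. This matches the form of the adverse event definition just before it. Seriousness alone then triggers the 24-hour form, expectedness is assessed afterwards by the Chief Investigator, and the ethics committee filter and the list of expected events do the work they were written for. Nothing else in the section needs to change.

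The cost is two words of protocol text. Measured against the later sentences, no extra SAE forms arise, because those sentences already require them. Measured against the literal definition, some would be added; the protocol gives no rate from which to count them, but the study has only 40 patients.

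### The exemption from ethics notification makes no exception for the study screw, so a serious screw reaction presenting as a wound complication or infection can miss the 15-day notice

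*Protocol*

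**What the plan says.** The Protocol section Adverse event management sends a serious event to the Research Ethics Committee within 15 days only if the Chief Investigator judges it both unexpected and related to the trial. It then sets a class of events aside: "Serious adverse events that may be expected as part of the surgical interventions, and that do not need to be reported to the main Research" (the sentence goes on to name that committee). Two groups are listed:

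- "complications of anaesthesia or surgery (e.g. wound complications, infection, damage to a nerve or blood vessel and thromboembolic events", an open list of examples;
- "secondary operations for infection, mal-union, non-union or for symptoms related to the metalwork".

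Neither group distinguishes events caused by the study screw from other events of the operation.

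On the device, the section Evidence for Bioabsorbable screws records a historical concern with "foreign body reactions, sterile abscess formation, sinus tract, fistula formation and osteolysis relating to some bioabsorbable implants, particularly PGA screws". The same section describes the study screw as one "which is a co-polymer of PLLA and PGA; poly L-lactide-co-glycolide (PLGA".

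**The concern.** This is a single-cohort study of one implant, in which notification of the ethics committee is the only outside safety notification that the section describes. The reactions the protocol itself associates with this class of implant appear at the wound, or look like infection. Those are the categories declared exempt. A serious reaction to the screw could therefore be handled, in full compliance with the text, as an expected complication of surgery.

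At stake is timely outside review while further patients are still receiving the screw. The data themselves are not lost.

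**Working it through.** There is no figure in the plan to reproduce. The check is a reading of the rule against the risks that the protocol names.

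**Step 1: the path of a serious event.** It is entered on the serious event form within 24 hours, the Chief Investigator confirms causality and expectedness, and events that are unexpected and related are notified within 15 days. The exempt list settles expectedness in advance for whatever falls inside it. The section gives no reference list of expected events specific to the screw.

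**Step 2: the named risks against the exempt categories.**

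| Event | Exempt category it could fall under | Strength of the reading |
|---|---|---|
| Sterile abscess, sinus tract, fistula | Wound complication, or infection until shown sterile | Natural |
| Foreign body reaction at the wound | Wound complication | Natural |
| Reoperation for any of these, treated as infected | Secondary operation for infection | Natural |
| Osteolysis | Complication of surgery, since the list is open | Possible |
| Reoperation for symptoms of the study screw | Symptoms related to metalwork | Ambiguous: the screw is a polymer |
| Reoperation for loss of syndesmosis reduction | Mal-union | Ambiguous: the term is not used this way elsewhere |

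The first three rows carry the point. They need no misfiling, only an ordinary reading of the list.

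**Step 3: relevance to this screw.** The background singles out PGA screws, and PGA is one component of the study co-polymer. It also cites a randomised trial of 168 patients with more foreign body reactions on PLLA screws, and PLLA is the other component. No rate is given for either, and the background says nothing on how often the co-polymer itself causes such reactions.

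**Step 4: what is lost and what is kept.**

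- Kept: every adverse event goes on the case report form. Wound review, secondary operations and adverse events are secondary outcomes, and complications are recorded at 2 weeks, 6 weeks, and 3, 6 and 12 months.
- Lost: the 15-day notice. Study Schedule plans inclusion from 01/12/2020 to 31/12/2024, which is 49 months. With 12 months of follow-up, the last visit falls at about the end of 2025, and the trial report comes after that. The protocol describes no interim safety report, so an early event could wait years for outside review instead of 15 days.

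**Step 5: size.** The expected number of affected events is 40 patients multiplied by the rate of serious screw reactions that present in an exempt form. The documents give no such rate, so no number follows. Calculations of how precisely 40 patients estimate a reaction rate do not bear on the matter, because the exemption removes no event from the complication count.

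**The case against.** The strongest reply is that the exemption governs one channel only. Capture on the case report form, the complication outcomes and the final report are untouched, and the Chief Investigator still assesses each serious event for causality. This stands, and it limits the point to outside notification. One qualification concerns the 24-hour form: the section defines a serious event as an unexpected one and then speaks of serious events that may be expected. Read literally, a listed event might not require that form. Listing on the case report form is unaffected.

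A second reply is that the remedy changes policy: the protocol anticipates these reactions in its background, so they could fairly be called expected. That is true. The carve-out asks for notification of device-related events even where they are foreseeable. It is a deliberate choice with a small price, and the sponsor should make it openly.

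Several stronger readings are tempting and are not supported:

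- A reader might infer that the list was written for metal fixation. The protocol puts real metal in many of these patients: "Typically a lag screw and one-third tubular neutralisation plate is used". It also uses the metal term for what the bioabsorbable screw avoids, namely "removing the need for removal of metalware in a second operation". Read literally, metalwork means the plate and lag screw, so removal of a symptomatic study screw is not clearly exempt.
- A reader might infer that a reoperation for loss of reduction is exempt as mal-union. Elsewhere the protocol speaks of reduction, malreduction, widening or diastasis of the syndesmosis. It pairs mal-union with non-union, which suggests fracture healing. The text is ambiguous at most.
- A reader might infer that the main safety signal goes unreported. The protocol ranks no signal as the main one, and the events are recorded and reported within the study.

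**Conclusion.** The point holds in a limited form. As written, the rule lets a serious reaction to the study screw that presents as a wound complication or infection, or leads to reoperation for infection, go without the 15-day ethics notice during recruitment. The consequence is delayed outside oversight, with no bias in the complication rate and no loss of data. Its frequency cannot be derived from the documents.

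The conclusion rests on four assumptions: such reactions present at the wound or as apparent infection; at least some meet the criteria for a serious event; the Chief Investigator applies the list as worded; and no other outside route exists. The last cannot be fully checked, since the recipient of the serious event form is removed from the text. This is a cheap improvement worth making; it is not a flaw that undermines the study.

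**What to change.** Add one sentence to Adverse event management: the exemption does not apply to serious events judged possibly related to the bioabsorbable screw, namely foreign body reaction, sterile abscess, sinus or fistula, osteolysis, screw failure, or reoperation for screw symptoms or for loss of syndesmosis reduction. State that metalwork in the exempt list means the non-study plate and screws. Record on the case report form whether each secondary operation is study-screw related, if it does not do so already (the form is not shown). The word unexpected in the definition of a serious event can be reconciled with the list of expected serious events in the same edit.

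The cost is a few lines of text, at most one new field, and a few more reports to the ethics committee. Treatment, visits and outcome measures do not change.
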